9.2 Secondary Efficacy Analyses

The following secondary efficacy analyses will be performed using the ITT and the respective PP populations where indicated.

BID Treatment Group:

TSQM domain scores at Visit 2, Visit 3 and Visit 4 will be summarized and presented descriptively for naïve patients. There are three domains which include effectiveness (3 items), convenience (3 items) and global satisfaction (3 items). (ITT/PP)

TSQM domain change from baseline (Visit 2) scores at Visit 3 and Visit 4 (secondary endpoint) will be summarized and presented descriptively for naïve patients using 2 different approaches, LOCF and no LOCF. Change from baseline scores will be analysed using a two-sided paired t-test or a non-parametric equivalent if warranted by the data. (ITT/PP)

Total qADAM scores at Visit 1, Visit 2, Visit 3 and Visit 4 will be summarized and presented descriptively for non-naïve patients. (ITT/PP)

Total qADAM change from baseline (Visit 1) scores at Visit 2, Visit 3 and Visit 4 will be summarized and presented descriptively for non-naïve patients using 2 different approaches, LOCF and no LOCF. Change from baseline scores will be analysed using a two-sided paired t-test or a non-parametric equivalent if warranted by the data. (ITT/PP)

Total qADAM scores at Visit 1, Visit 2, Visit 3 and Visit 4 will be summarized and presented descriptively for naïve patients. (ITT/PP)

Total qADAM change from baseline (Visit 1) scores at Visit 2, Visit 3 and Visit 4 will be summarized and presented descriptively for naïve patients using 2 different approaches, LOCF and no LOCF. Change from baseline scores will be analysed using a two-sided paired t-test or a non-parametric equivalent if warranted by the data. (ITT/PP)

Part A questions 5, 6, 7, 8, 9, 10 and 11 of the Patient Preference and Use Questionnaire at Visit 1 will be summarized and presented descriptively/categorically for non-naïve and naïve patients. (ITT)

TID Treatment Group:

TSQM domain scores at Visit 2, Visit 3, Visit 4 and Visit 5 will be summarized and presented descriptively for naïve patients. There are three domains which include effectiveness (3 items), convenience (3 items) and global satisfaction (3 items). (ITT/PP)

TSQM domain change from baseline (Visit 2) scores at Visit 3, Visit 4 and Visit 5 (secondary endpoint) will be summarized and presented descriptively for naïve patients using 2 different approaches, LOCF and no LOCF. Change from baseline scores will be analysed using a two-sided paired t-test or a non-parametric equivalent if warranted by the data. (ITT/PP)

Total qADAM scores at Visit 1, Visit 2, Visit 3, Visit 4 and Visit 5 will be summarized and presented descriptively for non-naïve patients. (ITT/PP)

Total qADAM change from baseline (Visit 1) scores at Visit 2, Visit 3, Visit 4 and Visit 5 will be summarized and presented descriptively for non-naïve patients using 2 different approaches, LOCF and no LOCF. Change from baseline scores will be analysed using a two-sided paired t-test or a non-parametric equivalent if warranted by the data. (ITT/PP)

Total qADAM scores at Visit 1, Visit 2, Visit 3, Visit 4 and Visit 5 will be summarized and presented descriptively for naïve patients. (ITT/PP)

Total qADAM change from baseline (Visit 1) scores at Visit 2, Visit 3, Visit 4 and Visit 5 will be summarized and presented descriptively for naïve patients using 2 different approaches, LOCF and no LOCF. Change from baseline scores will be analysed using a two-sided paired t-test or a non-parametric equivalent if warranted by the data. (ITT/PP)

Part A questions 5, 6, 7, 8, 9, 10 and 11 of the Patient Preference and Use Questionnaire at Visit 1 will be summarized and presented descriptively/categorically for non-naïve and naïve patients. (ITT)

ALL Treatment Group:

Total qADAM scores at Visit 1, Visit 2, Visit 3, Visit 4 and Visit 5 will be summarized and presented descriptively for non-naïve patients. (ITT/PP)

Total qADAM change from baseline (Visit 1) scores at Visit 2, Visit 3, Visit 4 and Visit 5 will be summarized and presented descriptively for non-naïve patients using 2 different approaches, LOCF and no LOCF. Change from baseline scores will be analysed using a two-sided paired t-test or a non-parametric equivalent if warranted by the data. (ITT/PP)

Total qADAM scores at Visit 1, Visit 2, Visit 3, Visit 4 and Visit 5 will be summarized and presented descriptively for naïve patients. (ITT/PP)

Total qADAM change from baseline (Visit 1) scores at Visit 2, Visit 3, Visit 4 and Visit 5 will be summarized and presented descriptively for naïve patients using 2 different approaches, LOCF

and no LOCF. Change from baseline scores will be analysed using a two-sided paired t-test or a non-parametric equivalent if warranted by the data. (ITT/PP)

Total qADAM scores at Visit 1, Visit 2, Visit 3, Visit 4 and Visit 5 will be summarized and presented descriptively for non-naïve and naïve patients combined. (ITT/PP)

Total qADAM change from baseline (Visit 1) scores at Visit 2, Visit 3, Visit 4 and Visit 5 will be summarized and presented descriptively for non-naïve and naïve patients combined using 2 different approaches, LOCF and no LOCF. Change from baseline scores will be analysed using a two-sided paired t-test or a non-parametric equivalent if warranted by the data. (ITT/PP)

Part A questions 5, 6, 7, 8, 9, 10 and 11 of the Patient Preference and Use Questionnaire at Visit 1 will be summarized and presented descriptively/categorically for non-naïve, naïve, and non-naïve and naïve patients combined. (ITT)

Various Treatment Groups:

Part B questions 5, 6, 7, 8, 9 and 12 of the Patient Preference and Use Questionnaire will be summarized and presented descriptively/categorically for non-naïve patients for the following groups and time points:

- BID at Visit 4 (ITT)
- TID at Visit 4 (ITT)
- TID at Visit 5 (ITT)

Part B questions 5, 6, 7, 8 and 11 of the Patient Preference and Use Questionnaire will be summarized and presented descriptively/categorically for naïve patients for the following groups and time points:

- BID at Visit 4 (ITT)
- TID at Visit 4 (ITT)
- TID at Visit 5 (ITT)

Natesto™ dosing frequency (BID/TID) by hypogonadism treatment status (naïve/non-naïve) assigned at Visit 4 will be summarized and presented categorically for non-naïve and naïve patients combined. (ITT/PP)

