2.2 Secondary Objectives

The secondary objectives of this study are to evaluate the following:

1. Improvement in hypogonadism symptoms
2. Patient treatment preference versus prior testosterone replacement therapy
3. Frequency of daily dose of Natesto™
4. Safety monitoring

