3.0 STUDY OVERVIEW

This is a phase 4, multi-centre study consisting of two study periods and a post study follow-up.

90-Day Treatment Period: With potential extension by 30 days for those patients requiring a dose increase, as determined by the treating physician. Participants receiving 122.5mg of Natesto™ (5.5 mg of testosterone) per nostril twice daily may have an increased daily dose adjustment on Day 90, based on their hypogonadism symptoms.

1-Day Study Completion Period: Patient will return to the site for examination, discussion of symptoms with physician and questionnaire completion. Serum testosterone levels will be determined for all patients on Day 90 (BID dose) and on Day 120 for the TID patients.

Post Study Follow-Up: All study patients will be followed up at Day 150 after the Treatment Phase to determine if they have continued using NATESTO and why (or why not?).

Schedule of Procedures

Study Phase	Treatment Period						
	Treatment Start	Efficacy Analysis				Post Study Follow Up	Early Withdrawal/Termination
	Day 0	Day 30 +/- 3 days	Day 60 +/- 3 days	End of Study: BID Patients Day 90 +/- 3 days	End of Study: TID Patients Day 120 +/- 3 days	Day 150 +/- 3 days	
Visit	1	2	3	4 ^a	5 ^b	6	
Location/Type	clinic	telephone	telephone	clinic	clinic	telephone	clinic
Study Procedures:							
Inclusion/exclusion criteria	X						
Informed consent	X						
Medical history	X			X	X		
Demographics	X						
Physical examination + nasal exam	X			X	X		X
Height and weight	X			X	X		X
Vital signs (HR, BP, RR, and temperature)	X			X	X		X
Serum total testosterone plus safety labs	X ^c			X	X ^d		X
Participant training on NATESTO administration	X						
Provide Study Drug Access Card for NATESTO	X						
Provide Pharmacy Prescription	X			X ^g			
Potential study drug daily dose increase to TID				X			
TSQM	X ^e	X	X	X	X		X
qADAM	X ^f	X	X	X	X		X
Patient Preference + Use	X			X	X		X
Concomitant medications	X	X	X	X	X		X
Assess adverse events	X	X	X	X	X		X
Assess voluntary treatment continuation						X	

- a. All patients are required to complete Visit 4
- b. Only patients assigned to NATESTO TID are required to complete Visit 5
- c. Naïve patients will require confirmation of hypogonadism by serum testosterone within the last 6 months
- d. Only patients who continued on TID
- e. TSQM to be completed by non-naïve patients only
- f. qADAM to be completed by all patients

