5.2 Secondary Efficacy Endpoints

The secondary efficacy endpoints are:

- change in satisfaction for each TSQM domain from Visit 2 (Day 30) to Visit 4 (Day 90) for naïve BID patients
- change in satisfaction for each TSQM domain from Visit 2 (Day 30) to Visit 5 (Day 120) for naïve TID patients
- change in total qADAM score from Visit 1 (Day 0) to Visit 4 (Day 90) for non-naïve BID patients
- change in total qADAM score from Visit 1 (Day 0) to Visit 5 (Day 120) for non-naïve TID patients
- change in total qADAM score from Visit 1 (Day 0) to Visit 4 (Day 90) for naïve BID patients
- change in total qADAM score from Visit 1 (Day 0) to Visit 5 (Day 120) for naïve TID patients
- change in total qADAM score from Visit 1 (Day 0) to Visit 5 (Day 120) for non-naïve ALL patients
- change in total qADAM score from Visit 1 (Day 0) to Visit 5 (Day 120) for naïve ALL patients
- change in total qADAM score from Visit 1 (Day 0) to Visit 5 (Day 120) for non-naïve and naïve ALL patients

- patient preference of therapy as measured by Part A of the Treatment Preference and Use Questionnaire at Visit 1 (Day 0) for the following groups of patients:
 - non-naïve and naïve ALL
 - non-naïve ALL
 - naïve ALL
 - non-naïve BID
 - naïve BID
 - non-naïve TID
 - naïve TID
- patient preference of therapy as measured by Part B of the Treatment Preference and Use Questionnaire for the following groups of non-naïve patients:
 - BID at Visit 4 (Day 90)
 - TID at Visit 4 (Day 90)
 - TID at Visit 5 (Day 120)
- patient preference of therapy as measured by Part C of the Treatment Preference and Use Questionnaire for the following groups of naïve patients:
 - BID at Visit 4 (Day 90)
 - TID at Visit 4 (Day 90)
 - TID at Visit 5 (Day 120)
- Natesto™ dosing frequency by hypogonadism treatment status (naïve/non-naïve) assigned at Visit 4 (Day 90)

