6.2 BID Intent-to-Treat (ITT) Population

The BID ITT population includes all patients who received at least one dose of study drug, are part of the BID treatment group and have a valid post-dose efficacy measurement at Visit 2 (Day 30) or Visit 3 (Day 60) or Visit 4 (Day 90). Data will be analysed using the BID ITT population as per the Table Mock-Up (TMU) document.

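### Post-treatment preference is tabulated only at Visits 4 and 5, so the answers the schedule collects at Early Termination enter no table the SAP provides for

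*SAP*

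**What the plan says.** Secondary objective 2 in section 2.2 is "Patient treatment preference versus prior testosterone replacement therapy".

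In the schedule in section 3.0, the row "Patient Preference + Use" is marked at Day 0, Day 90, Day 120 and in the column "Early Withdrawal/Termination". It is blank at Days 30, 60 and 150.

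Section 5.2 defines the post-treatment endpoints as "patient preference of therapy as measured by Part B of the Treatment Preference and Use Questionnaire for the following groups of non-naïve patients" and "patient preference of therapy as measured by Part C of the Treatment Preference and Use Questionnaire for the following groups of naïve patients". Each is followed by the same three entries: BID at Visit 4, TID at Visit 4, TID at Visit 5. Section 9.2 repeats those entries, all on the ITT set: "Part B questions 5, 6, 7, 8, 9 and 12 of the Patient Preference and Use Questionnaire will be summarized" for non-naïve patients and "Part B questions 5, 6, 7, 8 and 11 of the Patient Preference and Use Questionnaire will be summarized" for naïve patients. Part A is tabulated separately, at Visit 1.

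To be in the BID ITT set (section 6.2), a treated BID patient must "have a valid post-dose efficacy measurement at Visit 2 (Day 30) or Visit 3 (Day 60) or Visit 4 (Day 90"). Any one of those visits is enough.

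**The concern.** The questionnaire is not given between Day 0 and Day 90. For a patient who leaves before Visit 4, the Early Termination visit is the only occasion on which a preference formed on the study drug can be recorded. Sections 5.2 and 9.2 do not tabulate that occasion. The tables carry an ITT label, but in effect they describe patients who attended Day 90 or, for the TID Visit 5 table, Day 120.

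The matter bears most on non-naïve patients, who are the ones able to compare the study drug with an earlier testosterone therapy. Section 12.0 describes an open-label study without randomization, so there is no control arm in which the same selection would operate. If the decision to leave is related to preference, the reported percentage answers secondary objective 2 for stayers only.

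**Working it through.** The SAP states no dropout rate and no expected preference, so there is no figure to reproduce. The check has two parts.

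**1. Does any other section bring the Early Termination answer into a preference table?**

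- Section 7.1: the BID group is everyone who did not titrate to TID. A patient who leaves before Visit 4 is therefore BID.
- Section 6.2: with a valid Visit 2 or Visit 3 measurement, that patient is in the BID ITT set. A patient who leaves before Visit 2 is not.
- Section 7.2: Early Termination is a nominal time point of its own and is not mapped to Visit 4 or Visit 5.
- Section 7.3: LOCF is specified for TSQM and qADAM only. It could not help here, because no earlier post-treatment preference exists to carry forward.
- Section 8.0: data outside the table mock-up go to listings.
- Sections 10.2 to 10.5: laboratory, testosterone, vital sign and physical examination data are all tabulated at Early Termination. Preference is not.

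So nothing in the SAP text brings the answer in. Who is affected depends on when the patient leaves:

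| Time of leaving | Post-treatment preference in the tables |
|---|---|
| After Visit 2 or 3, before Visit 4 | None, although the patient can be in BID ITT |
| TID, between Visits 4 and 5 | Visit 4 answer kept; absent from the Visit 5 table |
| After the last scheduled treatment visit, before Day 150 | Kept in full, although section 7.4 calls this an early termination |

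**2. How much could it matter?**

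Let d be the share of non-naïve ITT patients who leave before Visit 4, p_stay the share of Visit 4 attenders who prefer the study drug, and p_leave that share among leavers. All three are assumptions. It is also assumed that every leaver answers at Early Termination, that the part given there is the post-treatment part, and that the answer reduces to preferring the study drug or not.

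With leavers included: P = (1 − d) × p_stay + d × p_leave.

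Overstatement when leavers are omitted: p_stay − P = d × (p_stay − p_leave).

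With p_stay = 60%, the Visit 4 table shows 60% whatever d is. With leavers included, P is:

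| d | p_leave = 10% | p_leave = 30% | p_leave = 60% |
|---|---|---|---|
| 5% | 57.5% | 58.5% | 60% |
| 10% | 55% | 57% | 60% |
| 20% | 50% | 54% | 60% |
| 30% | 45% | 51% | 60% |

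Over d = 5–30%, p_stay = 50–70% and p_leave = 10–30%:

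- Smallest: 0.05 × (50 − 30) = 1 percentage point.
- Largest: 0.30 × (70 − 10) = 18 percentage points.
- If p_leave = p_stay: 0.

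A 60% majority among stayers falls below half once d exceeds (60 − 50)/(60 − p_leave). That is 10/50 = 20% with leavers at 10%, and 10/30 = 33% with leavers at 30%.

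**The case against.** The strongest reply is that these are descriptive counts for a secondary endpoint. No test or success criterion rests on them, by-visit tables of observed answers are common, and a falling denominator would be visible. This stands, and it limits the weight of the point. It does not explain why a scheduled answer is left out of the tables when the safety data from the same visit are included.

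A reader might infer that the preference result is biased toward the study drug. The SAP does not show that. It gives no withdrawal rate, no reasons for withdrawal and no expected preference. The direction is plausible, but it depends on leavers being less favourable than stayers.

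A reader might also infer that everyone who leaves drops out of the result. That is too broad: a patient who leaves after Visit 4 keeps the Visit 4 answer. Nor does the prior-therapy argument reach naïve patients, who have no earlier therapy to go back to. For them the omission is one of completeness.

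The table mock-up is not at hand and might hold an Early Termination table. If so, sections 5.2 and 9.2 still do not provide for it. Finally, some patients will be lost to follow-up, as section 7.1 anticipates, and will give no answer at all. Using the Early Termination answers would not recover them, so the arithmetic above is an idealized case.

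**Conclusion.** The omission is real. Sections 5.2 and 9.2 leave out a post-treatment preference answer that the schedule collects, and no other section brings it in. ITT patients who leave before Visit 4 have no tabulated preference, and TID patients who leave between Visits 4 and 5 are missing from the Visit 5 table only.

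The effect on the result is conditional. Under the assumed ranges the non-naïve percentage would be overstated by 1 to 18 percentage points, with zero if leavers and stayers answer alike. None of these rates comes from the SAP. Because the endpoint is descriptive and the answers are already scheduled, this is an inexpensive improvement and does not threaten the main analysis.

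A separate inconsistency does not change this: for naïve patients section 5.2 names Part C and section 9.2 names Part B.

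**What to change.** - In sections 5.2 and 9.2, add Early Termination as a tabulated time point for post-treatment preference, as section 10 already does for the safety data.
- Add one supportive table with a single post-treatment answer per patient, taken from Visit 5, otherwise Visit 4, otherwise Early Termination. Present it over the ITT set by treatment status, with the number giving no answer as its own category.
- State which answer counts when a TID patient has both a Visit 4 and a later Early Termination answer. The order above takes Visit 4; the latest by date would be Early Termination.
- Keep the by-visit tables.

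Cost: SAP wording and one more table, with no new data collection. The supportive table pools answers given after unequal exposure, and its percentage may be less favourable to the study drug. Because it stays within the ITT set, patients who leave before Visit 2 remain outside it.

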6.6 BID Per-Protocol (PP) Population

The BID PP population includes all BID ITT patients who completed the 90-day (Visit 4) Treatment Period without any major protocol deviations. Data will be analysed using the BID PP population as per the Table Mock-Up (TMU) document.

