6.7 TID Per-Protocol (PP) Population

The TID PP population includes all TID ITT patients who completed the 120-day (Visit 5) Treatment Period without any major protocol deviations. Data will be analysed using the TID PP population as per the Table Mock-Up (TMU) document.

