7.0 DATA CONVENTIONS

7.1 Definitions

Visit 1 (Day 0) is defined as the day in which the patient provides informed consent and starts the study. All study days are determined relative to Visit 1 (Day 0).

End of treatment is defined as the day on which the last dose of treatment is taken. This date was not collected for this study.

End of study is defined as the last day on which data were collected from the patient. Using the Early Termination Visit eCRF, it is the date of early termination. Using the Visit 6 - Post Study Follow-Up (Day 150) eCRF, it is the post study follow-up date. Otherwise, it is the date of last contact, if the patient was lost to follow-up, or the date of death, if the patient died.

Baseline serum testosterone values will be defined as those values recorded on Visit 1 (Day 0). Naive patients were asked for 2 measurements (average used in analysis) and non-naive patients were asked for 1 measurement at Baseline (Visit 1/Day 0).

Serum Testosterone will be reported in (nmol/L). If value is reported in (ng/dL) then value will be multiplied by 0.0347 to convert to (nmol/L).

Testosterone collected in (pmol/L) will be considered Free Testosterone and will not be used in any analyses.

Hematocrit will be reported in (%). Values will be multiplied by 1 and if the value is less than 1 then the value will be multiplied by 100.

Total Cholesterol will be reported in (mmol/L). If value is reported in (mg/dL) then value will be divided by 38.67 to convert to (mmol/L).

LDL will be reported in (mmol/L). If value is reported in (mg/dL) then value will be divided by 38.67 to convert to (mmol/L).

HDL will be reported in (mmol/L). If value is reported in (mg/dL) then value will be divided by 38.67 to convert to (mmol/L).

Triglycerides will be reported in (mmol/L). If value is reported in (mg/dL) then value will be divided by 88.57 to convert to (mmol/L).

Hemoglobin will be reported in (g/L). If value is reported in (g/dL) then value will be divided by 0.1 to convert to (g/L).

ALT and AST will be reported in (U/L).

Study duration (days) will be defined as the (end of study date – date of informed consent + 1).

The ALL treatment group will be defined as patients who were either naïve or non-naïve.

The BID treatment group will be defined as patients who were either naïve or non-naïve and did not titrate to TID (Visit 5/Day 120).

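### The PP table of dosing frequency assigned at Visit 4 requires TID patients to complete Visit 5 but BID patients only Visit 4, and the ITT table has no stated rule for patients who left before the decision

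*SAP*

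**What the plan says.** Dosing frequency is secondary objective 3 in SAP 2.2. SAP 5.2 makes the endpoint Natesto "dosing frequency by hypogonadism treatment status (naïve/non-naïve) assigned at Visit 4 (Day 90"). SAP 9.2 tabulates it in two categories, in ITT and in PP: Natesto "dosing frequency (BID/TID) by hypogonadism treatment status (naïve/non-naïve) assigned at Visit 4 will be summarized and presented categorically". SAP 3.0 places the decision at the same visit: patients on twice-daily dosing "may have an increased daily dose adjustment on Day 90, based on their hypogonadism symptoms", and the schedule marks the possible increase at Visit 4 only.

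The populations used for this table are defined by other criteria:

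- SAP 6.6, BID PP: BID ITT patients "who completed the 90-day (Visit 4) Treatment Period without any major protocol deviations".
- SAP 6.7, TID PP: TID ITT patients "who completed the 120-day (Visit 5) Treatment Period without any major protocol deviations".
- SAP 7.1: "The BID treatment group will be defined as patients who were either naïve or non-naïve and did not titrate to TID (Visit 5/Day 120"). Reaching Visit 4 is not a condition.
- SAP 6.2, BID ITT: at least one dose, membership of the BID group, and a valid efficacy value at any one of Visits 2, 3 or 4.
- SAP 6.4, ITT: BID ITT and TID ITT together, with no third group.

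SAP 8.0 says that categorical variables are shown as counts and percentages. It lists a missing count for continuous variables but not for categorical ones.

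**The concern.** An endpoint fixed at Day 90 should not depend on what happens after Day 90. In PP it does, and for one category only. A patient moved to TID who leaves at Day 100 is removed although the assignment is on record. A patient kept on BID has no further condition to meet once Visit 4 is complete.

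The ITT table has a separate weakness. A patient who gives a Visit 2 score and leaves at Day 45 belongs to ITT, and under 7.1 can belong to it only as BID, although nobody made a dose decision for that patient. Section 9.2 does not say whether such a patient is counted as BID, shown as missing, or left out of the denominator.

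The endpoint is a simple proportion with no test attached, so no error rate is affected. But the proportion is the whole result for a named secondary objective, and its denominator determines it.

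**Working it through.** The SAP states no titration rate and no attrition rate, and section 4.0 sets about 100 participants without a calculation. There is no planned figure to reproduce, so the rates below are assumptions shown over a range.

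Notation:

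- p: share assigned TID among patients with a Visit 4 decision
- e: share of TID patients lost from PP between Visit 4 and Visit 5, by leaving or by a major deviation
- d: proportion of ITT patients leaving before Visit 4

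**PP.** With no other losses, a common Visit 4 rule gives p. The rules in 6.6 and 6.7 give p(1−e) / [p(1−e) + (1−p)].

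- p = 30%, e = 10%: 0.27 / (0.27 + 0.70) = 27.8%
- p = 30%, e = 20%: 0.24 / (0.24 + 0.70) = 25.5%
- p = 50%, e = 10%: 0.45 / (0.45 + 0.50) = 47.4%
- p = 50%, e = 20%: 0.40 / (0.40 + 0.50) = 44.4%
- e = 0: no change

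Deviation losses up to Visit 4 may differ between the groups. Let h be the share of BID patients lost that way, with none lost from TID before Visit 4, and p = 30%. Under a common Visit 4 rule the share is p / [p + (1−p)(1−h)]; under 6.6 and 6.7 both p terms are multiplied by (1−e).

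| h | Common Visit 4 rule | As defined, e = 10% | As defined, e = 20% |
|---|---|---|---|
| 0 | 30.0% | 27.8% | 25.5% |
| 10% | 32.3% | 30.0% | 27.6% |
| 20% | 34.9% | 32.5% | 30.0% |

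In every row the planned rule gives a lower TID share than the common rule. The PP share can still exceed p (32.5% against 30%), but that comes from BID losses that a common rule would also have.

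**ITT.** If patients who left before Visit 4 are counted as BID, or are unclassified but stay in the denominator, the TID percentage is p(1−d).

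- p = 30%: 27.0% for d = 10%, 24.0% for d = 20%
- p = 50%: 45.0% for d = 10%, 40.0% for d = 20%
- d = 0, or leavers removed from the denominator: no change

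**In patients (assumed).** Of 100 ITT patients, 20 leave before Visit 4 and 24 of the other 80 are assigned TID.

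- Among patients with a decision: 24/80 = 30.0%
- ITT with leavers in the denominator: 24/100 = 24.0%
- PP as defined, 22 of the 24 completing Visit 5: 22/(22+56) = 28.2%
- PP as defined, 19 of the 24 completing Visit 5: 19/(19+56) = 25.3%

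**A related ambiguity.** Section 7.1 ties titration to Visit 5: "and did not titrate to TID (Visit 5/Day 120"). It is unclear whether a patient moved to TID at Visit 4 who never reaches Visit 5 counts as TID. If such patients fell into BID, the TID share among patients with a decision would be p(1−e), which is 24.0% at p = 30% and e = 20%.

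**The case against.** A reader might infer that the SAP classifies every early leaver as BID in this table. It does not say so. The variable is the frequency assigned at Visit 4, and a Day 45 leaver has none. Section 7.2 says that data at the nominal time points are used and lists Early Termination separately, and 9.2 does not say that the table is built from the group label in 7.1. Such a patient may be meant to be missing. This part of the objection stands: the ITT fault is an unstated denominator, not a stated misclassification. The share is unaffected only if leavers also leave the denominator, which the SAP does not say either. The Table Mock-Up, not at hand, may settle it.

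A reader might also infer that both tables understate the share of patients needing TID. The documents do not support that. The endpoint is frequency assigned, not need, and patients who reached Visit 4 do not measure need either, since some leavers may have gone for lack of effect. At p = 30% and d = 20%, the share of all ITT patients who would have been assigned TID lies anywhere from 24%, if no leaver would have been, to 44% (0.24 + 0.20), if every leaver would have been.

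It can also be said that the PP share need not fall, because BID deviations can offset the TID losses. That is true of the overall PP figure but not of the effect of the unequal completion rule, as the table shows.

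Finally, the shift is small against sampling error: for 30% of 80 patients the 95% interval is about ±1.96 × √(0.3 × 0.7 / 80), or ±10 points. That limits the weight of the point. It is no reason to keep a distortion of known direction that costs almost nothing to remove.

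**Conclusion.** The PP fault is in the text. Sections 6.6 and 6.7 condition a Day 90 value on events after Day 90 in the TID category alone. Compared with a common Visit 4 rule, this can only lower the TID share: from 30% to 27.8% or 25.5% if 10% or 20% of TID patients are lost after Day 90 and there are no other PP losses.

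The ITT fault is conditional. Sections 6.2, 6.4 and 7.1 make an early leaver a BID patient, and 9.2 does not say how that patient enters this table. If leavers are tabulated as BID or kept in the denominator, p is reported as p(1−d).

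The size rests wholly on assumed rates and is zero where no such losses occur. The claim concerns the share assigned TID among patients with a decision and does not extend to how many patients needed it.

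**What to change.** In SAP 9.2, for this table only:

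- Apply completion of Visit 4 to both groups in the PP version, or drop the PP version.
- Report BID and TID as percentages of patients with a recorded Visit 4 assignment, whatever happened after Day 90.
- Show ITT patients who left before Visit 4 as a separate count labelled as having no Visit 4 decision.
- State that a patient assigned TID at Visit 4 counts as TID here whether or not Visit 5 took place.
- Describe the result as the share assigned TID, not the share needing it.

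The cost is SAP wording and one changed table, with no new data. The reported BID share may become slightly less favourable.
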